# 1 Introduction

## 1.1 Background

Prostate cancer is the most common non-skin cancer diagnosis among men in the United States, and accounted for 29% of all new cancer diagnoses and 9% of cancer deaths among American men in 2012 (1). The American Cancer Society has estimated that 241,740 patients were diagnosed with prostate cancer, and that 28,170 deaths occurred due to the disease in that year (1). The National Cancer Institute further estimates that 238,590 incident cases will be identified in 2013, and that 29,720 deaths will be attributable to prostate cancer (2). Accounting for current screening processes and estimates of incidence trends, 1 in 6 men in the United States will be diagnosed with prostate cancer in their lifetimes, and 1 in 33 will die from the disease (3).

Trends in prostate cancer incidence have closely paralleled the dissemination of screening and diagnostic technologies. The incidence increased dramatically between the mid-1970s and late 1980s as transurethral resection of the prostate (TURP) to treat benign prostatic hypertrophy (BPH) became increasingly common; by the mid-1980s, 50% of prostate cancer diagnoses were incidentally detected as a result of TURP procedures (3). In the early 1990s, implementation of regular PSA screening corresponded with a dramatic increase in prostate cancer incidence, followed by a compensatory decline in the past decade (1,3). Prostate cancer mortality has decreased steadily since the early 1990s, and a cumulative decrease of 39% was observed between 1991 and 2007 (1,3). Between 2001 and 2007, age-adjusted 5-year survival rates were 100% for local and regional prostate cancers, and 29% for distant cancers (1).

Although prostate cancer is exceedingly common in North America and Western Europe, it is substantially less so in Asia and South America (1, 4). This discrepancy is thought to be at least partially due to genetic susceptibility, and familial predisposition is estimated to account for 5-10% of all prostate cancers (1,4). Of note, African Americans experience the highest known incidence of prostate cancer in the world, 241 per 100,000, in contrast to 149 per 100,000 among white American men (1,4).

Advanced age is the most significant risk factor associated with prostate cancer diagnoses: approximately 97% of prostate cancers are diagnosed in men 50 years of age or older, and 60% are diagnosed in men aged 65 and above (1,4). Since 2004, however, prostate cancer incidence among men aged 65 and older has decreased by 2.7% per year, and has remained stable among men under 65 years of age (1).

Although current evidence is minimal, preliminary research has suggested that additional risk factors may affect the risk of prostate cancer diagnosis and death. Numerous observational studies have identified associations between obesity and an increased risk of prostate cancer incidence and mortality (5-7). Occupational exposures have been associated with elevated risk of prostate cancer in firefighters and pesticide applicators (8-10). Dietary characteristics such as

high intake of polyunsaturated fats, calcium, dairy products, and processed meats have all been shown to increase risk of prostate cancer (1,4,11,12).

## **1.2 Status and Limitations of Current Therapies**

Current treatment options for localized prostate cancer include active surveillance, radiation therapy (delivered as external beam radiation or brachytherapy), and radical prostatectomy (1,4,13,14). No statistically significant survival advantage has been reported with any one treatment option compared to the others, and treatment decisions are based on patients' symptomatic burden, comorbidities, stage of disease, and probability of treatment side effects (1, 4, 13-16).

Among patients with high-grade localized prostate cancer, radical prostatectomy is associated with substantial increases in overall survival (17). Over the past decade, robotic-assisted laparoscopic radical prostatectomy (RALRP) has surpassed open retropubic radical prostatectomy (RRP) as the most common surgical treatment for prostate cancer. RALRP now accounts for 80% of all radical prostatectomies performed in the United States (18,19). Although long-term outcomes data following RALRP are limited, available evidence suggests that mortality outcomes following RALRP and RRP are comparable (both are extremely low), and that RALRP may be associated with lower complication rates (19-21). Both perioperative (blood loss and transfusion requirements, postoperative pain, length of hospital stay, and 30-day mortality) and long-term follow-up (potency, continence, quality of life, biochemical recurrence, salvage therapy requirements, and overall and disease-free survival) outcomes associated with RRP have been well characterized (19,22,23).

Although there is no universal definition of a "large" prostate – threshold values in the published literature range from 50 to 100g – there is general consensus that large prostate size poses a therapeutic challenge for both surgeons and radiation oncologists (24-26). Of particular relevance to RALRP, larger prostate size limits mobility and visualization, and have been associated with longer procedure times and increased blood loss during surgery (22,23,27). Patients with larger prostate sizes are also more likely to experience poor postoperative functional outcomes, typically requiring more time to regain continence and achieving poorer sexual function (22,24).

The enhanced dissection capabilities of robotic surgery have the potential to mitigate the increased morbidity associated with operating on large prostate sizes (22). At present however, the technical challenges of operating on large prostates are compounded by poor visualization (22,23,27). Preoperative therapies that reduce prostate size may thus improve intraoperative visualization and consequently lead to reduced procedure times, decreased blood loss, and expedite return to continence and sexual function.

Androgen deprivation therapy (ADT) has been used to reduce prostate size prior to surgery and radiation treatment (28-32). ADT typically requires at least 3 months to achieve a reduction in

prostate size. However, there are significant side effects of treatment including bone and chest pain, rapid weight gain, cough, frequent/painful urination, headache, vision problems, depression and hormonal symptoms such as hot flashes, gynecomastia, testicular atrophy and impotence (28-32).

Although they allow better visualization and mobility, smaller prostates present challenges of their own. Numerous studies have reported statistically significant higher incidences of positive surgical margins in prostates smaller than 50g (22, 25, 33). Improving intraoperative visibility by reducing blood loss during RALRP may have a positive impact on surgical margin status for smaller prostate sizes.

In this study, we explore a new methodology for volumetric reduction of prostate along with concomitant reduction of vascularity of the prostate gland. Our hypothesis is that the prostate volumetric reduction along with reduced gland vascularity will result in a reduction of blood loss and improved visualization translating into superior surgical outcomes with regard to both short-term morbidity and long-term oncologic and functional outcomes.

### **1.3 Prostate Artery Embolization (PAE)**

Prostate artery embolization (PAE) was first reported in 2000 as a case study of a 76 year-old BPH patient with refractory hematuria (34). The patient underwent embolization with PVA particles, and by 5- and 12-month follow-up visits the patient's prostate was reduced by 52% and 62% of its pre-procedure size, respectively. This decrease in prostate size was accompanied by a decrease in PSA of approximately 90% by the 12-month visit.

The first animal trials of PAE were conducted in 6 beagles with Embosphere® Microspheres (BioSphere Medical, Roissy, France) (35). Immediately following the embolization procedures, retrograde urethrocytography and multiphasic, multislice, contrast-enhanced CT scans were obtained to document distribution of the microspheres and residual perfusion, and to perform 3-dimensional volumetric analysis. CT scans performed 1 month after PAE revealed appropriate distribution of the microspheres in the embolized territory with no evidence of non-targeted embolization. Stenosis of the prostatic urethra was reduced in all animals that received bilateral PAE, and decreased perfusion, cavitory necrosis and prostate volume reduction was evident following unilateral or bilateral PAE.

Sun and colleagues published the first animal study to evaluate the feasibility and safety of trans-arterial embolization (TAE) of the prostate in 16 healthy male pigs (36). All 16 animals underwent selective angiography, and 8 of the 16 then received PAE with Embosphere Microspheres. No significant difference in sexual desire or function was noted between the two groups ( $p=0.328$ ). At necropsy, urinary bladder, ureters, urethra, sigmoid colon, and rectum appeared to be normal in all animals. The prostate volume of the embolization group on histopathology evaluation was significantly decreased compared to the control group ( $p<0.001$ ).

Further studies in canine models yielded similar results. Jeon and colleagues showed that transcatheter arterial embolization with PVA particles can be used safely to reduce prostate volume in hormone-induced canine prostatic hyperplasia (37). In an additional study conducted in 7 dogs by the Sun group, 4 animals demonstrated significant reductions in prostate size while the other 3 appeared to have continued prostate growth (38). Intraprostatic cavities occupying 90-100% of the gland were identified in the 3 dogs that experienced an apparent increase in prostate size, and histopathological examination revealed little to no residual prostate tissue.

The first intentional treatment of BPH with PAE in humans was performed by Carnevale and colleagues (39). Two patients with acute urinary retention due to BPH refractory to selective  $\alpha$ -blockers underwent PAE with Embosphere Microspheres under local anesthesia. Both had long-term indwelling catheters and were waiting for surgery. Prior to embolization, both patients underwent digital rectal examination, urodynamic testing, prostate biopsies, transrectal ultrasound (TRUS) and pelvic MRI. Post-PAE the patients underwent repeat urodynamic testing, TRUS and MRI at 30, 90 and 180 day follow up visits.

The first patient, aged 67 with a history of hypertension, had a prostate estimated at 63gm by TRUS and 69gm by MRI with an intravesical prostate protrusion (IPP) of 9mm. Bilateral PAE was performed successfully without complications. The patient experienced mild retropubic pain for 24 hours, which was treated with non-opioid analgesics. He experienced no fever or hematuria and was discharged 3 days after the procedure. The patient was able to urinate spontaneously when his catheter was removed 15 days post PAE. At one month of follow-up his prostate was reduced by 33.3% and 39.1% by TRUS and MRI, respectively, IPP was reduced to 4mm, and post void residual urine volume (PVR) was 8mL. At 3 months post PAE the patient was urinating normally, IPP was unchanged, Post void residual (PVR) was reduced to 5mL, and prostate size reduction was 39.7% and 44.9% by TRUS and MRI, respectively. By 6 months post PAE, PVR was absent and prostate size was similar to that at 3 months.

The second patient was aged 68 years, with a history of atrial fibrillation and hypertension. TRUS showed a prostate of 51g and asymmetric hypertrophy of the right lobe with an IPP of 16mm. Pelvic MRI estimated prostate size at 54g and revealed a discrete 1.1cm avascular cystic node on the right, protruding at the bladder neck. Unilateral PAE of the right prostate arteries was performed because the left arteries could not be visualized.

The patient had no post-PAE symptoms, was discharged 3 days after the procedure, and was able to urinate spontaneously when the catheter was removed 10 days after embolization. At 1 month of follow-up the patient reported occasional nocturia, PVR was measured at 110mL, IPP was unchanged from baseline (at 16mm), and prostate size was reduced 16.9% and 24.1% by TRUS and MRI, respectively. MRI revealed that the avascular nodule had increased to 1.3cm. By 3 months of follow-up the patient was voiding normally, IPP remained unchanged, PVR was reduced to 68mL, prostate size reduction was 25.5% and 27.8% by TRUS and MRI, respectively, and the cyst persisted. The patient's condition was similar at 6 months of follow-up.

For both patients urine stream increased with time, accompanied by reduction of PVR and prostate size shrinkage that was sustained at 6 months. Reduction was greater in the patient who received bilateral embolization.

The same investigators published midterm follow-up data for these 2 patients (40). The prostate of the first patient, who underwent bilateral PAE, continued to decrease in size over time, with a reduction of 53.6% by MRI at 18 month follow up. The patient was continuing to void normally at 30 months post embolization.

The second patient, for whom it had only been possible to perform unilateral PAE, demonstrated an increase in prostate size at 18 months compared to imaging done at the 6 month follow up visit. MRI showed a 12.2% reduction from baseline at 18 months compared to 27.8% at 6 months. PVR had increased to 200 mL and IPP was 17mm. At both the 18- and 30-month follow-up visits the patient was continuing to void normally.

More recently, Carnevale presented outcomes of 40 PAE procedures in 39 patients (41). Eleven patients with acute urinary retention treated with indwelling catheters were enrolled in a Phase I/II study and treated with PAE. This group included the first 2 feasibility cases (Phase I, discussed earlier) plus 9 other patients (Phase II). After completion of this study 28 additional patients who were not managed with indwelling urinary catheters were treated. Evaluations at baseline, 1, 3, 6, and 12 months post procedure were performed by MRI, TRUS, urodynamic testing (baseline and every 12 months), PSA, International Prostate Symptom Score questionnaire (IPSS) and International Index of Erectile Function questionnaire (IIEF). Embolization was performed with Embosphere Microspheres under local anesthesia. Clinical success was achieved in 10 of the 11 phase I/II patients (91%), with patients able to urinate spontaneously after catheter removal and no recurrence of lower urinary tract symptoms (LUTS) during 16-45 months of follow-up.

The single clinical failure was a patient who was embolized twice but still was not able to urinate spontaneously. He was referred for surgery and treated by TURP. Minor adverse events included diarrhea, light rectal bleeding (2-3 tsp), hematuria, anal burning sensation, retropubic pain and dysuria. Only non-opioid analgesics were required for pain management. Among the remaining 38 patients in whom PAE successfully reduced LUTS, one case of bladder ischemia was recognized retrospectively. The patient experienced no pain or urinary retention, but a defect was seen in the bladder wall by MRI at 30 days of follow-up. The ischemic area resolved spontaneously, and was not seen at future MRI surveillance.

Among the first 11 patients, average PSA levels dropped from 10.1ng/ml at baseline to 3.5ng/mL at month 3 ( $p=0.003$ ), and average prostate size reduction was approximately 30% by MRI ( $p=0.002$ ) and TRUS ( $p=0.004$ ). It was not possible to obtain IPSS and IIEF scores at baseline because all patients had indwelling catheters prior to PAE, but these scores improved from first measurement at 30 days post PAE throughout a year of follow-up, with changes in the IPSS

being statistically significant ( $p=0.04$ ). Average response from the quality of life question of the IPSS went from 6 (terrible) at baseline to 1.1 (pleased) at the 30 day follow-up, and continued at  $<1$  (delighted) from 3-12 months of follow-up. Average changes in urodynamic tests from baseline to 12 months were as follows: urine flow ( $Q_{max}$ ) improved from 4.2mL/sec to 10.8mL/sec ( $p=0.009$ ), detrusor muscle pressure ( $P_{det}$ ) reduced from 85.7 to 51.5 ( $p=0.007$ ), and PVR decreased from 160.6mL to 60mL ( $p=0.04$ ).

In the subsequent 28 patients without acute urinary retention or indwelling catheters at time of treatment, average IPSS scores decreased from 20.3 (severe) at baseline to 1.7 (mild) at 90 days of follow-up, and prostate size reduction averaged 26.4% by MRI in the same period.

Urodynamic test results were also notable in this group:  $Q_{max}$  increased from an average 8.0ml/sec at baseline to 17.4mL/sec at 90 days. Overall clinical success for all 39 patients, defined as LUTS improvement and ability to urinate spontaneously, was 97.5%.

None of the described studies reported new incidence of erectile dysfunction following PAE (39-41). This leads us to believe that sub-selective embolization of prostatic arteries does not cause embolization of feeding vessels to neurovascular bundles and hence does not lead to impotence or incontinence after the embolization procedure.

To date, no reported study has evaluated selective embolization of prostatic arteries as a pre-operative tool before radical prostatectomy.

The promising results described above led to development of this study, which aims to assess whether reduction in volume and vascularity of the prostate gland by pre-surgery prostate artery embolization improves surgical, functional and oncologic outcomes following robot-assisted laparoscopic radical prostatectomy (RALRP).

## **2 Study Objectives**

### **2.1 Primary Objective**

The primary study objective is to evaluate estimated blood loss (EBL) during robot-assisted laparoscopic radical prostatectomy (RALRP) among patients who receive pre-operative PAE using Embosphere Microspheres and those that do not.

### **2.2 Secondary Objectives**

The key secondary objectives are to assess the outcomes listed below and to compare the results for patients who receive PAE and those that do not:

1. Change in hemoglobin on RALRP post operative day (POD) 1 compared to baseline
2. Change in hematocrit on RALRP post operative day (POD) 1 compared to baseline
3. Change in prostate volume between baseline and Visit 3 (6 weeks  $\pm$  2 weeks post PAE) as determined by MRI in patients who receive PAE
4. Blood transfusion requirements during RALRP
5. RALRP duration in minutes
6. Length of hospital stay for RALRP
7. Presence or absence of a complete surgical margin around the entire tumor as determined by histopathology examination post RALRP
8. Biochemical recurrence of prostate cancer as determined by PSA levels post RALRP at 1 year follow up
9. Return to continence post RALRP as assessed by the pad weight test.
10. RALRP related adverse events
11. Erectile function compared to baseline as assessed by the IIEF post RALRP at 1 year follow up.

Additional secondary objectives are to assess outcomes listed below for patients that receive PAE:

12. Change in PSA between baseline and Visit 3 (6 weeks  $\pm$  2 weeks post PAE)
13. PAE related adverse events
14. Histologic changes in the prostate after PAE

### **3 PAE Patient Population**

#### **3.1 Inclusion Criteria**

Patients must meet all of the following inclusion criteria in order to be entered into the study:

1. Patient is 45-79 years old
2. Patient has signed informed consent
3. Patient must have biopsy-proven prostate adenocarcinoma with localized disease
4. Patient must be a candidate for robot-assisted radical prostatectomy (RALRP)
5. Patient has a prostate size >40 grams

### 3.2 Exclusion Criteria

Patients meeting any of the following exclusion criteria may not be entered into the study:

1. Active urinary tract infection
2. History of life threatening allergy to iodinated contrast agents
3. Any known condition that limits catheter-based intervention or is a contraindication to embolization (eg shunt or adverse arterial anatomy)
4. Patient is unable to undergo MRI imaging
5. Cardiac condition including congestive heart failure or uncontrolled arrhythmia, uncontrolled diabetes mellitus, significant respiratory disease, or known immunosuppression which required hospitalization within the previous 6 months.
6. Baseline serum creatinine level  $> 1.8$  mg/dL
7. Baseline hemoglobin  $< 8.0$  g/dL
8. Active cystolithiasis or prostatitis
9. History of pelvic irradiation or radical pelvic surgery
10. Known major iliac arterial occlusive disease
11. Confirmed or suspected bladder cancer
12. Urethral strictures, bladder neck contracture, or other bladder or urethral pathology that could limit catheterization
13. Previous rectal surgery (other than hemorrhoidectomy) or history of rectal disease if the therapy or patient evaluation may potentially cause injury to sites of previous rectal surgery, e.g. if a transrectal probe is used
14. Previous pelvic irradiation or radical pelvic surgery
15. Previous prostate surgery, balloon dilatation, stent implantation, laser prostatectomy, hyperthermia, or any other invasive treatment to the prostate
16. Prior transurethral resection of the prostate or other invasive therapies
17. Coagulation disturbances not normalized by medical treatment
18. Acute urinary retention
19. Hypersensitivity to gelatin products
20. Any contraindication to embolization, including intolerance to vessel occlusion procedures, vascular anatomy/blood flow that precludes catheter placement or embolic agent injection, presence/likely onset of vasospasm, presence/likely onset of hemorrhage, severe atheromatous disease, feeding arteries smaller than distal branches, arteriovenous shunt, and collateral vessel pathways endangering normal territories during embolization or pelvic inflammatory disease

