### **9.5.3 Additional Secondary Efficacy Outcomes – PAE Patients Only**

#### **9.5.3.1 Change in Prostate Volume**

An analysis of the change in prostate volume between baseline (pre-PAE) and Visit 3 as determined by MRI will be performed. Each PAE patient will have their prostate volume measured at both timepoints and the change will be calculated. Summary data will be presented for both timepoints and the change from baseline, including 95% confidence intervals.

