### **9.6.2 Concomitant Medications**

Concomitant medications data will be presented in the data listings.

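### No entry criterion addresses androgen deprivation, so shrinkage in a man part-way through it would be counted as change after PAE

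*Combined protocol and SAP*

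**What the plan says.** **Eligibility.** Section 3.1 has 5 inclusion criteria, one of them on gland size: "Patient has a prostate size >40 grams". Section 3.2 has 20 exclusions. Those on earlier treatment are no. 15 ("Previous prostate surgery, balloon dilatation, stent implantation, laser prostatectomy, hyperthermia, or any other invasive treatment to the prostate"), no. 16 ("Prior transurethral resection of the prostate or other invasive therapies"), and nos. 9 and 14, the latter reading "Previous pelvic irradiation or radical pelvic surgery". No criterion mentions ADT. There is no section on prohibited medication or washout, and section 6 does not list starting ADT as a reason for withdrawal.

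**ADT.** Section 1.2 states: "Androgen deprivation therapy (ADT) has been used to reduce prostate size prior to surgery and radiation treatment". On timing it says "ADT typically requires at least 3 months to achieve a reduction in" prostate size, and it lists impotence among the side effects.

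**Outcomes.** Section 9.5.3.1 says: "An analysis of the change in prostate volume between baseline (pre-PAE) and Visit 3 as determined by MRI will be performed". The PSA change is handled in the same way. Both are summarised with 95% confidence intervals in PAE patients only. Appendix A2 gives controls one prostate MRI, at baseline.

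**Medications.** Current medications are recorded at baseline in both arms (section 5.1) and concomitant medications at later visits, including Visit 3 for PAE patients and surgery for both arms (sections 5.4 and 5.5). Section 9.4 reports medications as a patient characteristic, and section 9.6.2 says: "Concomitant medications data will be presented in the data listings". No analysis in section 9 uses them.

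**The concern.** The protocol introduces PAE as a new way to reduce gland volume before surgery, having just described ADT as an existing way to do so. A man on ADT may enter if his gland still exceeds 40 g. If it is shrinking because of the drug, the change from baseline to Visit 3 mixes the two effects. The design cannot separate them, because there is no second MRI in controls and no rule for handling an ADT user.

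At stake are the two single-arm outcomes meant to show that PAE shrinks the gland and changes PSA. There are also side effects on other comparisons. IIEF baseline is taken before PAE or before RALRP (section 9.5.2.9), so impotence from ADT could already be present in it and distort the change. Section 3 is headed as the PAE population, and Appendix A2 gives controls a matching assessment where Appendix A1 has an eligibility assessment. Nothing therefore keeps ADT users out of the control arm or balances them between arms.

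**Working it through.** The plan states no figure on this point, and section 9.2 says that no formal sample size calculation was made, so there is nothing to reproduce. The check has three steps.

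**1. How long is the window?**
- Baseline MRI to PAE: 0-4 weeks (section 5.2).
- PAE to Visit 3: 6 ± 2 = 4-8 weeks (section 5.4).
- PAE to RALRP: 10 ± 2 = 8-12 weeks (section 5.5).
- Baseline MRI to Visit 3 MRI: 0 + 4 = 4 weeks up to 4 + 8 = 12 weeks.
- Baseline MRI to RALRP: 0 + 8 = 8 weeks up to 4 + 12 = 16 weeks.

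**2. Whose ADT matters?** Section 1.2 puts shrinkage at no less than 3 months, about 13 weeks.
- ADT started at or after the baseline MRI: at most 12 weeks by Visit 3, so typically no visible reduction yet. It could act by surgery, at up to 16 weeks.
- ADT already under way at the baseline MRI: the 13-week point falls inside the window if the lead time is at least 13 − 12 = 1 week for the longest interval, or 13 − 4 = 9 weeks for the shortest.
- ADT given for so long that the gland has stopped shrinking: little is added to the change from baseline.

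The bias in the Visit 3 volume change therefore comes from men part-way through ADT whose glands are still shrinking between the scans.

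**3. How large could it be?** Let k be the number of such men among the 10 treated and d the drug-related shrinkage between the two MRIs, assumed to add to the PAE effect. Then

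shift in mean shrinkage = k × d / 10.

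The documents give neither k nor d. I assume d = 10-30%. For scale, section 1.3 cites a mean reduction of 26.4% by MRI at 90 days in 28 PAE patients. Section 9.5.3.1 does not say whether change is absolute or in percent. Percent is used here to match that series.

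| k | d = 10% | d = 20% | d = 30% | Share of 26.4% |
|---|---|---|---|---|
| 1 | 1.0 point | 2.0 points | 3.0 points | 3.8% to 11.4% |
| 2 | 2.0 points | 4.0 points | 6.0 points | 7.6% to 22.7% |
| 3 | 3.0 points | 6.0 points | 9.0 points | 11.4% to 34.1% |

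For example, k = 1 and d = 30% give 1 × 30 / 10 = 3.0 points, and 3.0 / 26.4 = 11.4%. With no such man in the analysis, the term is zero.

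**The case against.** The other side has several good points.

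- **The data are there.** Medications are recorded in both arms, reported as a characteristic and listed. With 10 treated men, any ADT user could be found afterwards. This stands, but it does not close the gap: removing patients from a group of 10 after seeing the results, with no rule set beforehand, is weak evidence.
- **The outcomes are modest.** Volume and PSA change are secondary and descriptive, without a test, in a proof-of-concept study. Histology of particle distribution and tissue change also bears on whether PAE worked (section 5.5). This limits the consequence.
- **ADT users may be rare.** Section 1.2 does not list ADT among the main options for localized disease and stresses its side effects. The documents do not show that users are expected among these candidates. They do describe its use before surgery, so the case is not remote.

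A reader might also infer more than the documents support:

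- *That any ADT user inflates the result.* Step 2 of the working shows otherwise.
- *That each user adds a full 3 points.* This needs 30% drug-related shrinkage between the scans. The documents give about 30% only for PAE, not for ADT, so 3 points is the top of an assumed range.
- *That a biased result is likely.* If 5-10% of candidates used ADT, the chance of at least one among 10 would be 1 − 0.95^10 = 0.40 to 1 − 0.90^10 = 0.65. That prevalence is not in the documents, and the calculation counts users of any kind, not only those still shrinking.
- *That the gap covers other size-reducing drugs.* ADT is the only drug that the documents describe as shrinking the prostate.
- *That the exclusions bar invasive treatment alone.* Nos. 9 and 14 also bar pelvic irradiation.

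**Conclusion.** The concern holds in a limited form. The plan has no entry rule on ADT and no rule for analysing men who receive it. The volume analysis as written would count shrinkage in a man part-way through ADT as change after PAE, and would do the same with any accompanying fall in PSA. Each such man adds 1-3 percentage points to the mean shrinkage of 10 patients, assuming 10-30% drug-related shrinkage that adds to the PAE effect. How many such men would enter cannot be derived from the documents.

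A reader might conclude that the primary comparison of blood loss is compromised. The documents do not support that. Blood loss would be affected only if ADT use differed between arms. That is possible, because matching uses AUA risk group alone, but nothing shows that it is expected.

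**What to change.** 1. Add an entry criterion, applied to both PAE and control patients, that excludes men with current or recent ADT. The sponsor should set and justify the look-back interval. The 3 months in section 1.2 describes onset of shrinkage, not recovery after ADT ends, so it does not justify an interval by itself. The criterion should select patients only and carry no instruction to stop any treatment.
2. Prespecify a sensitivity analysis that repeats the volume, PSA and IIEF summaries without any man whose recorded medications show ADT at baseline or before RALRP. For the paired IIEF comparison, state that his matched partner drops out with him.

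The cost is a few ineligible candidates, with slightly slower recruitment, and one extra analysis of data already collected.
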